7.4.4. Duration of Disease Control

The duration of disease control is the time from the first dose date to the first objective response of PD (by irRECIST v1.1 or modified Lugano Classification [Cheson et al 2014]), death, or last tumor assessment date (if PD/death not present), for subjects with best overall response of SD or better. In the case of SD, measurements must meet the SD criteria at least once after study entry at a minimum interval of 56 days. Median duration of disease control and CIs will be estimated using the Kaplan-Meier method. Subjects who have SD or better at the clinical data cutoff or discontinuation will be right-censored at last valid response assessment date before starting any new anticancer therapy. The duration of disease control evaluation will be performed separately for each treatment group and no statistical comparison will be made.

7.4.5. Overall Survival

For OS analysis, the Kaplan-Meier method will be used to estimate the survival time distribution and the median survival of each treatment group. Subjects will continue to be followed-up for OS even after a positive PFS analysis and a final analysis of OS will be conducted after OS data are mature (eg, \sim 70% or more than 52 subjects are dead).

7.4.6. Largest Percentage Reduction in Sum of Diameters of Target Lesions

For each subject, the percentage change from baseline in sum of the longest diameters of target lesions will be derived for each postbaseline period at which a valid target lesion assessment is provided. The best percentage change for each subject will be derived for waterfall plots and potential exploratory analyses.

Per RECIST criteria, target lesions considered "too small to measure" will be assigned a default value of 5 mm for purposes of this analysis. Likewise, target lesions identified as "not present" at postbaseline assessments will be assigned 0 mm for this analysis. In the event a target lesion is unaccounted for at a particular postbaseline timepoint, that is, assessment missing or NE, then the overall sum of target lesions will not be evaluable for that postbaseline timepoint.

7.4.7. Other Efficacy Analyses

7.4.7.1. Eastern Cooperative Oncology Group Performance Status

Subjects' ECOG performance status and changes in status at scheduled assessment times will be summarized.

7.4.8. Subgroup Analyses for Efficacy Endpoints

Subgroups will be formed based on the following subject characteristics and baseline variables for subjects with different tumor types whose data are available.

- For all tumor types:
 - PD-L1 status (positive, negative)

8. SAFETY AND TOLERABILITY

The list of table and listing displays are provided in Appendix E.

8.1. General Considerations

The analyses for this section will be provided using the safety evaluable population. Summary tables may be replaced with listings when appropriate. For instance, an AE frequency table may be replaced with a listing if it only contains a few unique preferred terms reported on relatively few subjects.

8.2. Adverse Events

8.2.1. Adverse Event Definitions

A TEAE is any AE either reported for the first time or worsening of a pre-existing event after first dose of study drug. Analysis of AEs (as discussed below) will be limited to TEAEs, but data listings will include all AEs regardless of their timing to study drug administration.

Adverse events will be tabulated by the MedDRA preferred term and system organ class. Severity of AEs will be described and graded using the NCI Common Terminology Criteria for Adverse Events (CTCAE) v4.03. The CTCAE reporting guidelines and grading details are available on the Cancer Therapy Evaluation Program website (NCI 2010).

A grading (severity) scale is provided for each AE term. If the toxicity is not included in the CTCAE v4.03 criteria, it will be rated on a scale of 1 to 4 as follows: 1 = mild, 2 = moderate, 3 = severe, and 4 = life-threatening. All toxicities will be graded based on the worst level reached, not the level they may have reached if they had not been treated. When the intensity of an AE changes over time for a reporting period (eg, between visits), each change in intensity will be collected as an AE until the event resolves. Only the worst grade will be reported in AE summaries. Also, the Grade 3 or higher AEs will be reported in a summary table to display all higher-intensity AEs.

The subset of AEs considered by the investigator to be related to epacadostat or pembrolizumab will be considered to be treatment-related AEs. If the investigator does not specify the relationship of the AE to study drug, then the AE will be considered to be treatment-related. The incidence of AEs and treatment-related AEs will be tabulated. Serious TEAEs will also be tabulated.

Any missing onset date, causality, or severity must be queried for resolution. Unsolved missing values will be handled according to the following rules:

- An unsolved missing causality will be considered treatment related.
- An unsolved missing severity will be identified as an unknown severity.

For purposes of analysis, all AEs will be considered TEAEs unless the AE can unequivocally be defined as not treatment emergent. Therefore, an unsolved missing onset date will be considered treatment emergent, with the following exceptions:

- If the stop/resolution date is before the first dose administration date on Day 1, then the AE will be considered as not being treatment emergent.
- If both the month and day are missing, and the last day of the year is before the first dose administration date on Day 1, then the AE will not be considered treatment emergent.
- If only the day is missing, and the last day of the month is before the first dose administration date on Day 1, then the AE will not be considered treatment emergent.
- If only the day is missing, and the first day of the month is after the first dose administration date on Day 1, then the AE will be considered treatment emergent.

8.2.2. Adverse Event Summaries

An overall summary of AEs by treatment group will include the following:

- Subjects who had a TEAE
- Subjects who had a Grade 3 or higher TEAE
- Subjects who had a serious TEAE
- Subjects who had a fatal TEAE
- Subjects who had a TEAE leading to dose interruption of INCB024360
- Subjects who had a TEAE leading to dose interruption of MK-3475
- Subjects who had a TEAE leading to dose interruption of INCB024360 and MK-3475
- Subjects who had a TEAE leading to dose reduction of INCB024360
- Subjects who had a TEAE leading to discontinuation of INCB024360
- Subjects who had a-TEAE leading to discontinuation of MK-3475
- Subjects who had a TEAE leading to discontinuation of INCB024360 and MK-3475
- Subjects who had a treatment-related (INCB024360 or MK-3475) TEAE
- Subjects who had a INCB024360-related TEAE
- Subjects who had a MK-3475-related TEAE
- Subjects who had a Grade 3 or higher treatment-related (INCB024360 or MK-3475) TEAE
- Subjects who had a treatment-related (INCB024360 or MK-3475) serious TEAE
- Subjects who had a fatal treatment-related (INCB024360 or MK-3475) TEAE
- Subjects who had a treatment-related (INCB024360 or MK-3475) TEAE leading to dose interruption of INCB024360

- Subjects who had a treatment-related (INCB024360 or MK-3475) TEAE leading to dose interruption of MK-3475
- Subjects who had a treatment-related (INCB024360 or MK-3475) TEAE leading to dose interruption of INCB024360 and MK-3475
- Subjects who had a treatment-related (INCB024360 or MK-3475) TEAE leading to dose reduction of INCB024360
- Subjects who had a treatment-related (INCB024360 or MK-3475) TEAE leading to discontinuation of INCB024360
- Subjects who had a treatment-related (INCB024360 or MK-3475) TEAE leading to discontinuation of MK-3475
- Subjects who had a treatment-related (INCB024360 or MK-3475) TEAE leading to discontinuation of INCB024360 and MK-347

The following summaries will be produced by MedDRA term (if ≤ 10 subjects appear in a table, then a listing may be appropriate):

- Summary of Treatment-Emergent Adverse Events by MedDRA System Organ Class and Preferred Term
- Summary of Treatment-Emergent Adverse Events by MedDRA Preferred Term in Decreasing Order of Frequency
- Summary of Treatment-Related (Epacadostat or Pembrolizumab) Adverse Events by MedDRA System Organ Class and Preferred Term
- Summary of Treatment-Related (Epacadostat or Pembrolizumab) Adverse Events by Preferred Term in Decreasing Order of Frequency
- Summary of Grade 3 or Higher Treatment-Emergent Adverse Events by MedDRA System Organ Class and Preferred Term
- Summary of Grade 3 or Higher Treatment-Emergent Adverse Events by MedDRA Preferred Term in Decreasing Order of Frequency
- Summary of Treatment-Emergent Adverse Events With a Fatal Outcome by MedDRA System Organ Class and Preferred Term
- Summary of Serious Treatment-Emergent Adverse Events by MedDRA System Organ Class and Preferred Term
- Summary of Serious Treatment-Emergent Adverse Events by MedDRA Preferred Term in Decreasing Order of Frequency
- Summary of Treatment-Emergent Adverse Events Leading to Any Dose Interruption by MedDRA System Organ Class and Preferred Term
- Summary of Treatment-Emergent Adverse Events Leading to Discontinuation of Any Study Drug by MedDRA System Organ Class and Preferred Term

- Summary of Treatment-Emergent Adverse Events Leading to Any Dose Reduction by MedDRA System Organ Class and Preferred Term
- Summary of Treatment-Emergent Adverse Events of Special Interest by Category and Preferred Term (AEOSI)

The sponsor-defined, immune-related adverse events of special interest (AEOSIs) and events of clinical interest (ECIs) are provided in Appendix C and Appendix D, respectively.

8.3. Clinical Laboratory Tests

8.3.1. Laboratory Value Definitions

Laboratory values and change from baseline values will be summarized descriptively by visit. The baseline value will be determined using the last nonmissing values collected before the first dose. For baseline laboratory values with the same date and time, additional rules may be provided after consultation with the medical monitor to delineate which value will be defined as baseline.

Laboratory test values outside the normal range will be assessed for severity based on CTCAE grade or similar criteria where clinical intervention is required for CTCAE grading. See Appendix B for laboratory grading criteria. The incidence of abnormal laboratory values and shift tables relative to baseline will be tabulated.

8.3.2. Laboratory Value Summaries

Clinical laboratory tests, including hematology and serum chemistry (see Appendix A), will be performed for each subject during the study in accordance with Table 13 in Protocol Amendment 10.

If specific safety issues arise, additional unscheduled laboratory tests/analyses may be performed at the discretion of the investigator.

All test results and associated normal ranges from central laboratories will be reported in SI units. All tests with numeric values will have a unique unit per test. Any laboratory test results and associated normal ranges from local laboratories will be converted to SI units. For the limited number of cases where the associated normal ranges from a local laboratory cannot be obtained despite due diligence, a set of standard normal ranges based on documented reference ranges will be applied to facilitate reporting the test results.

Laboratory parameters identified in Table 10 will be summarized. Shift tables based on worst postbaseline value recorded will use all postbaseline values. Other laboratory parameters collected will only be listed in an appendix to the Clinical Study Report in their original units without SI conversions. A detailed listing of the serum chemistry, hematology, and urinalysis tests is provided in Appendix A.

Panel	Parameter
Serum chemistry	Albumin, alkaline phosphatase ^{a,b} , ALT ^{a,b} , AST ^{a,b} , amylase, bicarbonate, BUN, calcium, chloride, creatinine, glucose, iron, lactate dehydrogenase, phosphorus, potassium, serum or plasma lipase, sodium, total bilirubin ^{a,b} , direct bilirubin, total protein, uric acid
Lipid	Total cholesterol, triglycerides, LDL, HDL, CRP ^b
Hematology	Hemoglobin, hematocrit, platelet count, red blood cell count, reticulocyte count, WBC ^b , basophils, eosinophils, lymphocytes ^b , monocytes, neutrophils ^b
Endocrine monitoring	ACTH ^c , serum cortisol ^c , LH, prolactin ^c , TSH ^c , free T4 ^c , T3 ^c , serum testosterone ^c
Urinalysis	Color and appearance, pH and specific gravity, bilirubin, glucose, ketones, leukocytes, nitrite, occult blood, protein, urobilinogen
Pregnancy test	Female subjects of childbearing potential only require a serum test at screening; pregnancy tests (serum or urine) should be repeated if required by local regulations
Coagulation	PT, aPTT, INR
Serology	HBsAG, HBsAG antibody, HBc, HCV antibody, HCV-RNA, HBV-DNA, HCV genotype, HCV viral load (for subjects with HCC only), anti-HDV, anti-HBe, HBV viral load, anti-HBc (total), HBeAg (for subjects with HCC who are HBsAg+ or anti-HBc+, anti-HBs-, HBsAg- viral load < 100 IU/mL only)
Other	CA 125 (ovarian cancer only), CEA (gastric cancer only), AFP (HCC only)

Table 10:Laboratory Parameters To Be Summarized

^a Summaries of LFTs will be performed on a weekly basis instead of by cycle.

^b Line graph and box-and-whisker plots will be provided.

^c Only normal-high-low shift tables will be provided.

Numeric laboratory values will be summarized descriptively, and non-numeric test values will be tabulated.

For test results that will be summarized with available normal ranges, the number and percentage of subjects with the laboratory values being low (but never high), normal, high (but never low), and both low and high will be calculated for each test. Laboratory values with greater than or less than signs will require medical monitor review. Laboratory ranges with greater than or less than signs will be handled as follows: if only an upper limit exists, for example, < 200, then the range will be (0,199.99); similarly, if only the lower limit exists, for example, > 0, then the range will be (0.001, 9999).

This shift summary will be produced for each test for the safety population. The denominator for the percentage calculation will use the number of subjects in the baseline category (ie, low, high, normal, missing) as the denominator for the percentage in each of the categories during the treatment period.

For all gradable laboratory parameters identified in Table 10, the values will be classified into grade levels corresponding to CTCAE v4.03 criteria. For specific laboratory values requiring clinical intervention to grade, the classification according to the quantitative component will be provided. See Appendix B for laboratory grading criteria.

The number and percentage of subjects with the laboratory values of Grade 1, 2, 3, or 4 will be calculated for each treatment according to the largest treatment-emergent worsening of

laboratory grade. Separate summaries for abnormally high and abnormally low laboratory values will be provided when the laboratory in question has both high and low grading criteria. For instance, if a subject has a baseline fasting glucose of 210 mg/dL, maximum fasting glucose after starting treatment of 245 mg/dL, and minimum fasting glucose after starting treatment of 52 mg/dL, then the subject will be counted as follows:

- The subject will be counted as a Grade 2 "Glucose decreased" in summaries of hypoglycemia because the subject was not hypoglycemic at study entry but became hypoglycemic after treatment.
- The subject will not count as a "Glucose increased" in summaries of hyperglycemia because the subject met the numeric requirements for Grade 2 hyperglycemia at baseline (fasting glucose value > 160 to 250 mg/dL) and did not increase in grade after starting treatment.

In cases where differentials of hematology parameters are obtained without corresponding absolute count data, efforts will be made to investigate if the conversion to an absolute value will lead to additional abnormalities. This will be discussed with the clinical team regarding appropriate documentation and action.

8.4. Vital Signs

Vital signs, including systolic blood pressure, diastolic blood pressure, pulse, respiration rate, and body temperature, will be taken with subjects in the seated position during the study in accordance with Table 12 in Protocol Amendment 10. Change and percentage change from baseline will be calculated using the last nonmissing value before first dose of study drug (Day 1) as the baseline value.

Incidences of clinically notable vital sign abnormalities are defined in Table 11. The abnormal values for subjects exhibiting clinically notable vital sign abnormalities will be listed along with their assigned treatment group. Alert vital signs are defined as an absolute value outside the defined range and percentage change from baseline greater than 25%.

Parameter	High Threshold	Low Threshold
Systolic blood pressure	> 155 mmHg	< 85 mmHg
Diastolic blood pressure	> 100 mmHg	< 40 mmHg
Pulse	> 100 bpm	< 45 bpm
Body temperature	> 38°C	< 35.5°C
Respiratory rate	> 24 breaths/min	< 8 breaths/min

 Table 11:
 Criteria for Clinically Notable Vital Sign Abnormalities

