15. Known history of human immunodeficiency virus (HIV) (HIV 1/2 antibodies).
16. Live attenuated vaccine within 30 days before the first dose of study treatment. Examples of live vaccines include, but are not limited to, the following: measles, mumps, rubella, chicken pox, yellow fever, rabies, Bacillus Calmette–Guérin (BCG), and typhoid vaccine. Seasonal influenza vaccines for injection are generally killed virus vaccines and are allowed; however, intranasal influenza vaccines (eg, FluMist®) are live attenuated vaccines and are not allowed.
17. Monoamine oxidase inhibitors within the 21 days before screening or any concurrent use of a prohibited medication listed in Section 5.13.
18. Any history of SS after receiving 1 or more serotonergic drugs.
19. Presence of a gastrointestinal condition that may affect drug absorption.
20. Use of systemic corticosteroids. **Exceptions:** Doses  $\leq$  10 mg/day are permitted (see Section 5.12) and use for radiographic procedures is permitted.

21. History or presence of an abnormal electrocardiogram (ECG) which, in the investigator's opinion, is clinically meaningful. Subjects with screening QTc interval > 480 ms are excluded. For subjects with an intraventricular conduction delay (QRS interval 120 ms), the JTc interval may be used in place of the QTc with sponsor approval. Subjects with left bundle branch block are excluded. Subjects with QTc prolongation due to a pacemaker may enroll if the JT is normal or with medical monitor approval.
22. History or current evidence of any condition, therapy, or laboratory abnormality that might confound the results of the study, interfere with the subject's participation for the full duration of the study, or is not in the best interest of the subject to participate, in the opinion of the treating investigator.
23. Known psychiatric or substance abuse disorders that would interfere with cooperation with the requirements of the study.
24. Immediate family member (self, spouse, or child) who is investigational site or sponsor staff directly involved with this study, unless prospective institutional review board (IRB) approval (by chair or designee) is given allowing exception to this criterion for a specific subject.
25. Known allergy or reaction to any component of either study drug or formulation components, including severe ( $\geq$  Grade 3) hypersensitivity to pembrolizumab and/or any of its excipients.

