8.5. Electrocardiograms

Twelve-lead ECGs will be obtained for each subject during the study in accordance with Table 12 in Protocol Amendment 10. The baseline for each parameter is the average of all available values collected at screening, Day -1, and Day 1 predose. A table of clinically significant ECG abnormalities and a listing of 12-lead ECG values will be reported in the abbreviated CSR. Electrocardiogram results will be reviewed for clinically notable

abnormalities according to predefined criteria (see Table 12). Number and percentage of subjects with alert ECG values (outliers), defined as the absolute value outside the defined range (see Table 12) and percentage change from baseline greater than 25% (30% for QRS interval), will be summarized.

Parameter	High Threshold	Low Threshold
QTcF ^a	> 460 msec	< 295 msec
PR	> 220 msec	< 75 msec
QRS	> 120 msec	< 50 msec
QT	> 500 msec	< 300 msec
RR	> 1500 msec	< 600 msec

 Table 12:
 Criteria for Clinically Notable Electrocardiogram Abnormalities

^a QTcF (Fridericia correction).

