3.2.19	Summary of Treatment-Emergent Adverse Events Leading to Any Dose Interruption by MedDRA System Organ Class and Preferred Term	Safety Evaluable	X
3.2.20	Summary of Treatment-Emergent Adverse Events Leading to Discontinuation of Any Study Drug by MedDRA System Organ Class and Preferred Term	Safety Evaluable	X
3.2.27	Summary of Treatment-Emergent Adverse Events of Special Interest by Category and MedDRA Preferred Term	Safety Evaluable	X
3.3 Labora	atory		
3.3.1.1	Summary of Laboratory Values - Hematology	Safety Evaluable	Х
3.3.1.2	Summary of Laboratory Values - Chemistry	Safety Evaluable	Х
3.3.1.3	Summary of Laboratory Values – Endocrine Monitoring	Safety Evaluable	Х
3.3.2.1	Shift Summary of Hematology Values - to the Worst Abnormal Value	Safety Evaluable	X
3.3.2.2	Shift Summary of Chemistry Values - to the Worst Abnormal Value	Safety Evaluable	Х
3.4 Vital S	igns		
3.4.1	Summary of Systolic Blood Pressure	Safety Evaluable	Х
3.4.2	Summary of Diastolic Blood Pressure	Safety Evaluable	Х
3.4.3	Summary of Pulse	Safety Evaluable	Х
3.4.4	Summary of Body Temperature	Safety Evaluable	Х
3.4.5	Summary of Respiration Rate	Safety Evaluable	Х

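### The added 25%-change condition empties the SAP alert tier for body temperature and makes the promised QTcF alert count too low

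*SAP*

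**What the plan says.** SAP 8.4 has two tiers for vital signs.

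- **Notable values.** These are defined by the Table 11 limits alone (temperature above 38 °C or below 35.5 °C). "The abnormal values for subjects exhibiting clinically notable vital sign abnormalities will be listed along with their assigned treatment group".
- **Alert values.** "Alert vital signs are defined as an absolute value outside the defined range and percentage change from baseline greater than 25" percent. The same percentage applies to all five vital signs. "Change and percentage change from baseline will be calculated using the last nonmissing value before first dose of study drug (Day 1) as the baseline".

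SAP 8.5 is built in the same way. ECGs are reviewed against Table 12 (QTcF above 460 msec, QT above 500 msec on the high side). Alert values, also called outliers, need a Table 12 breach and a "percentage change from baseline greater than 25% (30% for QRS interval), will be summarized" as number and percentage of subjects. "The baseline for each parameter is the average of all available values collected at screening, Day -1, and Day 1 predose". For the report itself, "A table of clinically significant ECG abnormalities and a listing of 12-lead ECG values will be reported in the abbreviated CSR".

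Protocol 3.3 sets the entry limit: "Subjects with screening QTc interval > 480 ms are excluded". Protocol 9.4.3 commits to flagging and tabulating clinically significant abnormal values by predefined criteria.

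SAP Appendix E plans Table 3.4.4, "Summary of Body Temperature", a summary of clinically significant ECG abnormality (Table 3.5.9), and listings of vital signs (2.9.1) and ECG values (2.10.1). It names no table of alert values in either domain.

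**The concern.** One percentage is applied to quantities that vary on very different relative scales. Pulse or respiratory rate can plausibly change by a quarter. Body temperature in °C cannot, and for QTcF a quarter of baseline is a very large prolongation. Because both conditions must hold, the stricter one decides, and for these two parameters that is almost always the percentage, not the limit printed in the table.

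A zero in a temperature alert row would look like an observation, although the rule could give no other result. On the ECG side, 8.5 promises a count. That count would leave out subjects beyond the 460 msec limit, and it would be least sensitive in those who start with the longest QTcF, which is the wrong way round for an outlier screen.

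**Working it through.** The SAP states no expected alert rate, so there is no figure to reproduce. The check is direct arithmetic on the rule. I read the percentage change as applying in either direction.

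**Formula.** With baseline b and high limit H, a high alert needs a value above the larger of H and 1.25 × b. The percentage is the stricter condition whenever b > H / 1.25. A low alert with limit L needs a value below the smaller of L and 0.75 × b.

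**Body temperature (H = 38 °C, L = 35.5 °C, Table 11).** The percentage is the stricter condition above 38 / 1.25 = 30.4 °C, so at every plausible baseline.

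- b = 35.5: alert above 44.4 °C
- b = 36.5: alert above 45.6 °C or below 27.4 °C
- b = 37.0: alert above 46.25 °C or below 27.75 °C
- b = 38.0: alert above 47.5 °C

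A reading of 42 °C is a rise of 15.1% from 36.5 °C. It would be an alert only from a baseline below 42 / 1.25 = 33.6 °C. The result also depends on the unit: computed in Fahrenheit, a 25% rise from 36.5 °C corresponds to 50.1 °C. The baseline range of 35.5 to 38.0 °C is my assumption, but the conclusion is the same throughout it.

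**QTcF (H = 460 msec, Table 12).** The percentage is the stricter condition above 460 / 1.25 = 368 msec.

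| Baseline (msec) | Alert only above (msec) | Rise needed (msec) |
|---|---|---|
| 368 | 460 | more than 92 |
| 380 | 475 | more than 95 |
| 400 | 500 | more than 100 |
| 420 | 525 | more than 105 |
| 440 | 550 | more than 110 |
| 480 | 600 | more than 120 |

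Below 368 msec the rise needed is 460 − b, which is more than 92. Above 368 it is 0.25 × b, also more than 92. So no rise under 92 msec is counted from any baseline. A value v counts only from a baseline below v / 1.25: 461 msec from below 368.8, and 500 msec from below 400.

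Two cases show the ordering. A change from 380 to 476 msec (+96, or 25.3%) counts. A change from 440 to 540 msec (+100, or 22.7%) does not, although both the value and the rise are larger.

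**QT (H = 500 msec, Table 12).** The percentage is the stricter condition above 500 / 1.25 = 400 msec.

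**How often a given QTcF value would count.** The documents give no baseline distribution. I assumed normal baselines with mean 390 to 420 msec and SD 15 to 25 msec, truncated at 480. The share of baselines from which a value is an alert, P(b < v / 1.25), is:

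- 461 msec: 0 to 20%
- 481 msec: 1 to 42%
- 501 msec: 10 to 76%
- 520 msec: 40 to 96%
- 550 msec: 80 to 100%

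These shares treat the on-treatment value as independent of baseline, which probably flatters the rule.

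**The case against.** The strongest reply is that the alert tier is supplementary. A temperature of 38.1 °C is notable under Table 11 and is to be listed. ECGs are reviewed against Table 12 without any percentage, every ECG value is listed, and Table 3.5.9 summarises clinically significant abnormalities. Under Protocol 7.5.6, clinically significant ECG findings after consent are recorded as adverse events, which are then graded and tabulated. SAP 8.4 defines alert vital signs but promises no count of them. Section 10.1 points to Appendix E for the outputs of the abbreviated report, and that appendix has no alert table.

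All of this stands, and it rules out several stronger inferences. A reader might conclude that fever cannot be flagged at all, or that the limits in Tables 11 and 12 have been disabled. Neither follows, because the notable tier uses those limits with no percentage. A reader might also conclude that QTcF prolongation is almost never flagged, or that alert counts will be near zero whatever happens. That does not follow for QTcF: a value just over 500 msec still counts from baselines up to about 400 msec, and under the assumed distributions 550 msec counts from most.

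The reply does not remove the defect. Section 8.5 still promises a number and percentage of subjects under the double condition, and it is the only Table 12 criterion for which a count is promised. No named output counts subjects with temperature above 38 °C or QTcF above 460 msec. Appendix E's silence leaves it unclear whether the promised ECG count will be produced; it does not correct the rule.

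**Conclusion.** The alert rule is wrong as written for two kinds of parameter. For body temperature the tier is empty at any plausible baseline. For QTcF the 25% condition replaces the 460 msec limit at every baseline above 368 msec, rises under 92 msec are never counted, and values of 461 to 500 msec are counted only from baselines below about 369 to 400 msec. Sensitivity falls as baseline QTcF rises.

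These results need only the stated rule, the limits in Tables 11 and 12, and plausible baseline temperatures. The 600 msec figure takes a QTcF baseline equal to the highest admissible screening QTc. The actual baseline is an average, and Protocol 7.5.6 allows either Fridericia or Bazett correction. The percentage shares for individual QTcF values rest on assumed baselines and show only a range.

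The defect is confined to the alert classification and matters most for the ECG counts promised in 8.5. Severity is modest, because this is a supplementary safety display.

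**What to change.** - **SAP 8.4:** drop the percentage condition for body temperature and use the Table 11 limits alone.
- **SAP 8.5:** drop the percentage condition for QTcF and QT. Count subjects with a post-baseline value beyond the Table 12 limit that was not present at baseline, and summarise the absolute change from baseline in msec. Any cut-points for that change should be prespecified by the sponsor.
- **Other parameters:** keep the percentage condition for blood pressure, pulse and respiratory rate, and for PR, QRS and RR.
- **SAP 8.4, 8.5 and Appendix E:** state which tier, notable or alert, each table and listing uses, and add the ECG count to Appendix E if it is to be reported.

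The cost is SAP wording and a small programming change. No new data are needed and patient care is not affected.
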